7.4.1.1. Lipid Panel and Apolipoproteins

A fasting lipid panel will be collected at the times listed in the [Schedule of Activities](#). The lipid panel will consist of the following measurements:

- Total cholesterol, low density lipoprotein cholesterol (LDL-C), high density lipoprotein cholesterol (HDL-C), non-HDL-C and triglycerides.
- ApoB and ApoA-1 will also be included at Day 1 and Week 26 visits as well as the glycemic rescue visit and early termination visit.

LDL-C will be calculated, using the Friedewald equation. If the triglycerides are over 400 mg/dL, the laboratory will measure LDL-C directly. Non-HDL-C will be calculated as (total cholesterol - HDL-C). If LDL-C is measured directly on a Day 1 sample, the central laboratory will perform direct LDL-C measurements on subsequent samples for that subject.

7.4.1.2. Urinary Albumin:Creatinine Ratio

A urine sample will be collected at the times listed in the [Schedule of Activities](#) (for measurement of the urinary albumin:creatinine ratio (mg/g)). These samples will be used to assess the change in the urinary albumin:creatinine ratio throughout the trial. Samples should

not be obtained if the subject is menstruating, has vigorously exercised within 24 hours or had fever or an active infection within 2 days of the visit.

7.4.2. Vital Signs (Sitting Blood Pressure and Pulse Rate)

Vital sign measurements include a triplicate measurement of sitting blood pressure and pulse rate. Blood pressure and pulse rate will be measured using an automated, oscillometric blood pressure measuring device at all time points noted in the [Schedule of Activities](#). Site personnel should use the same blood pressure measuring device throughout the trial for each subject.

The following method should be used to record sitting blood pressure and pulse rate for subjects in triplicate:

- Subjects will refrain from nicotine-containing products and/or ingesting caffeine for at least 30 minutes preceding the measurements.
- Subjects should be seated in a chair with their back supported, feet flat on the floor and arm bared (free of restrictions such as rolled up sleeves) and supported at heart level.
- The appropriate cuff size must be used to ensure accurate measurement. Each subject's cuff size should be noted in his/her source file to assure the same cuff size is used throughout the trial.
- Measurements should be taken on the same arm at each visit (preferably the non-dominant arm).
- Measurements should begin after at least 5 minutes of rest.
- The three measurements of both the blood pressure and pulse rate must be taken approximately 2 minutes apart with the triplicate set recorded in the source document and CRFs.
- Assessment of pulse rate can be manual (rather than using an automated device); however, when done manually, pulse rate must be measured in the brachial/radial artery for at least 30 seconds.

Other procedures should not be performed during the time of the blood pressure and pulse rate measurements.

7.4.3. Postural (Orthostatic) Blood Pressure and Pulse Rate

On the S3, Day 1, Week 6 and Week 26 visits, duplicate measurements of supine and standing blood pressure and pulse rate will be taken in order to evaluate postural changes in blood pressure and pulse rate. These measurements will be in addition to the sitting blood pressure and pulse rate measurements taken on these clinic visits (except for S3 visit).

Measurement of postural blood pressure and pulse rate will also occur at the glycemic Rescue Visit.

Postural blood pressure changes will be measured according to the following procedure:

- Subject in supine position for a minimum of 5 minutes.
- Measure blood pressure and pulse rate in the supine position in duplicate (at least 1 minute apart).
- Stand subject and measure blood pressure and pulse rate in the standing position in duplicate according to the following instructions. The first measurement of standing blood pressure and pulse rate will be measured after at least 1 minute of standing. The second measurement of standing blood pressure and pulse rate will be measured after the subject has been standing for at least 3 minutes.

7.4.4. Electrocardiogram, (12-lead ECG)

Single, supine 12-lead ECGs will be obtained at the pre-defined nominal time points outlined in “[Schedule of Activities](#)”. ECG equipment with an instruction manual will be provided by the Sponsor.

- Subjects will refrain from nicotine-containing products and/or ingesting caffeine for at least 30 minutes preceding the procedure.
- 12-lead ECGs should be performed after the subject has rested quietly for **at least 10 minutes** in a supine position.

12-lead ECGs should be obtained prior to the nominal time assessment of blood pressure, and pulse rate as well as prior to blood collection.

The screening ECG should be read and interpreted at the investigative site. ECGs performed at Day 1 and time points after randomization should be reviewed at the investigative site for subject safety monitoring, as well as electronically transmitted to a central vendor for reading and interpretation centrally. The Investigator is responsible for retaining all copies of the ECG reports.

Subject demographic information will be made available to the central scoring site that will provide results on heart rate (beats per minute [BPM]), overall interpretation, rhythm type, and heart rate intervals PR, QRS, QT, QTcB, and QTcF (msec), along with any comments.

7.4.5. Review of Self-Monitoring Glucose Logs

The site must review and assess the glucose values recorded on the self-monitoring glucose logs completed by the subjects at **each** site visit subsequent to the S2 visit.

7.4.6. Review of Hypoglycemia Assessment Logs

The site must review the hypoglycemia assessment logs completed by the subjects at **each** site visit subsequent to the S2 visit. Based on this information, an assessment of any symptomatic occurrence of hypoglycemia must be undertaken and appropriate decisions should be made by the Investigator.

7.4.6.1. Management of Hypoglycemia

Subjects will be instructed to check fingerstick glucose when they have symptoms consistent with hypoglycemia such as hunger, headache, dizziness, light headedness, sweating, palpitation, tachycardia, tremulousness, irritability, blurred vision, and disorientation. Subjects should be instructed to call the site should these symptoms occur and/or worsen before next visit.

A subject should be discontinued from the investigational product if they have repeated (2 or more episodes since the prior visit) FPG or fingerstick glucose <50 mg/dL (<2.8 mmol/L) with or without symptoms of hypoglycemia or ≤ 70 mg/dL (≤ 3.9 mmol/L) with symptoms of hypoglycemia, and without a reasonable explanation (such as increased physical activity or skipped meal).

Any episode of hypoglycemia must be captured on the Hypoglycemic Adverse Event Form of the CRF (refer to [Section 6.1.1](#)). For definition of hypoglycemic episode and severity categorization, refer to Section 7.4.6.1.1 below.

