- u. The Future Biomedical Research (FBR) informed consent must be obtained before FBR samples are drawn. The FBR sample for DNA analysis should be obtained pre-dose, at Day 1/Visit 4, as the last sample drawn, on subjects who qualify for randomization, but may be obtained at a later date during the trial after the FBR informed consent is obtained. The plasma and serum samples for FBR should be collected at Day 1 (pre-dose), Week 26, Week 104 or Early Termination Visit, and Rescue Visit (if applicable). The plasma and serum samples for FBR should be collected at all time points, even if the pre-dose or other time point was not collected.
- v. The sample(s) for measurement of bone biomarkers and PTH should not be collected if the investigational product has been discontinued for >7 days prior to the collection of the sample(s).
- w. Subjects will be seen by a dietician or qualified healthcare professional for dietary and exercise counseling at S2 Visit only; at other visits subjects should be asked about their diet and exercise which may be done by other appropriate site personnel evaluating the subject.
- x. Subjects should be educated on the symptoms of hyperglycemia (eg, polyuria, polydipsia) at S2.
- y. Assess AEs, SAEs, hypoglycemia assessment log as well as potential clinical events for adjudication (See [Sections 7.4.6, 7.8, 8](#) for additional detail).

TABLE OF CONTENTS

| | |
|--|----|
| LIST OF TABLES | 24 |
| LIST OF FIGURES | 24 |
| APPENDICES | 25 |
| 1. INTRODUCTION | 30 |
| 1.1. Indication..... | 30 |
| 1.2. Background | 30 |
| 1.3. Efficacy of Ertugliflozin..... | 31 |
| 1.4. Safety Information for Ertugliflozin and Other SGLT2 Inhibitors | 31 |
| 1.5. Rationale for Study and Design | 33 |
| 1.5.1. Rationale for Dose Selection of Ertugliflozin | 34 |
| 1.5.2. Rationale for Future Biomedical Research..... | 35 |
| 2. STUDY OBJECTIVES, HYPOTHESES AND ENDPOINTS | 35 |
| 2.1. Objectives and Hypotheses | 35 |
| 2.2. Endpoints..... | 38 |
| 2.2.1. Primary Endpoint..... | 38 |
| 2.2.2. Secondary Endpoints | 38 |
| 3. STUDY DESIGN..... | 39 |
| 4. SUBJECT SELECTION..... | 43 |
| 4.1. Inclusion Criteria..... | 43 |
| 4.2. Exclusion Criteria..... | 45 |
| 4.3. Randomization Criteria | 50 |
| 4.4. Life Style Guidelines..... | 51 |
| 4.4.1. Dietary Restrictions | 51 |
| 4.4.2. Physical Activities | 51 |
| 4.4.3. Alcohol, Caffeine and Tobacco | 51 |
| 4.4.4. Female Contraception..... | 52 |
| 4.4.4.1. Females– Non-childbearing Potential | 52 |

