5.3.5.1. Administration of Glimepiride/Matching Placebo

The dose of glimepiride/matching placebo will be initiated at 1 mg/day (or matching placebo for 1 mg tablet) starting on the day of the Week 26 visit for subjects who were not rescued in Phase A, and only if subject's fasting fingerstick glucose (FFSG) at Week 26 visit is ≥ 110 mg/dL (6.1 mmol/L).

If the subject's FFSG at Week 26 visit is < 110 mg/dL (6.1 mmol/L), the subject will not receive glimepiride/matching placebo at the Week 26 visit.

All subjects will continue with investigational product (ertugliflozin/placebo) during Phase B, regardless of whether a subject does or does not initiate glimepiride/matching placebo at Week 26.

For subjects started on glimepiride/matching placebo 1 mg at Week 26, at the Week 30 visit, the dose of glimepiride/matching placebo will be increased to 2 mg once daily (QD), if deemed appropriate by the Investigator based on the subject's self-monitoring blood glucose measurements and assessment of risk of hypoglycemia. Assessment of glimepiride dosing will then take place at subsequent clinic visits (ie, Weeks 39, 52, 65, 78, and 91). Further up-titration of glimepiride will be made in increments of 2 mg/day, with the maximum dose (6 or 8 mg QD) based upon the local label of glimepiride. Subjects may remain on 1 mg/day if appropriate based on finger-stick glucose monitoring.

Subjects who did not have glimepiride/matching placebo initiated at the Week 26 visit may have glimepiride/matching placebo initiated (with 1 mg dose) at any subsequent visit, if their FFSG is no longer < 110 mg/dL (6.1 mmol/L), and subsequently uptitrated, as described above. Down-titration is allowed at any time during the trial, as needed, in order to avoid hypoglycemia.

It is recommended that the dose of glimepiride be administered with breakfast or the first main meal of the day.

If any adjustment in the administration of glimepiride/matching placebo is necessary between scheduled visits, an unscheduled visit to the site should be performed.

In case of hypoglycemia:

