If a subject experiences episodes of unexplained hypoglycemia (ie, not explained by missed meals or excess physical activity), the subject's glimepiride/matching placebo should be down-titrated to a dose determined appropriate by the Investigator. In general, glimepiride should be down-titrated by 2 mg/day (eg, 6 mg to 4 mg or 4 mg to 2 mg), or more rapidly, as considered appropriate by the Investigator. In subjects receiving 2 mg/day the dose should be reduced to 1 mg/day in case of hypoglycemia. Subjects on glimepiride/matching placebo 1 mg who experience unexplained hypoglycemia should interrupt glimepiride/matching placebo and may continue in the trial off of glimepiride/matching placebo. If unexplained hypoglycemia continues to occur after glimepiride/matching placebo is interrupted, the subject should be considered for discontinuation from the blinded investigational product

according to [Section 6.7.2](#) – Reason for Discontinuation from Investigational Product or From the Study.

If a subject has had glimepiride/matching placebo interrupted or down-titrated, and re-initiation or up-titration of therapy is considered appropriate, then re-initiation and/or up-titration of glimepiride/matching placebo may be performed through the end of Phase B according to the guidelines used for initial up-titration.

Note: If glimepiride/matching placebo is re-initiated, the dose should not be up-titrated beyond the dose at which hypoglycemia originally occurred.

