6.4.2. Week 39 (Visit 10) through Week 91 (Visit 14)

Visits following Week 30 have a visit window of ± 14 days relative to Day 1. The procedures for Visits 10-14 are described in this section.

Additional procedures are required for Week 52 (V11), which are further defined in [Section 6.4.3](#), respectively.

Following the preceding visit and within the corresponding visit window, subjects will return to the site after a minimum **10-hour fast** (except water) for V9-14. At these visits, the following procedures will be completed:

- Update concomitant medications since last visit.
- Assess treatment compliance with investigational product and blinded glimepiride/placebo therapy (if applicable), and counsel subject for non-compliance, as needed.
- Measure body weight in duplicate [refer to [Section 7.2](#)].
- Collect triplicate measurements of sitting blood pressure and pulse rate [refer to [Section 7.4.2](#)].
- Conduct inquiry about any spontaneously reported AEs by asking the subjects to respond to a non-leading question such as "how do you feel?" Assess potential clinical events for adjudication [refer to [Section 7.8](#)].
- Review self-monitoring blood glucose and Hypoglycemia Assessment Logs completed by the subject [refer to [Section 7.4.6](#)].
- Diet and exercise monitoring (see [Section 6.1.2](#)).

- Perform a fasting finger stick blood glucose assessment at the clinic.
- Obtain blood **and** urine specimens for:
 - Clinical laboratory tests [refer to [Section 7.4.1](#)] including chemistry; hematology (only at Week 52 and Week 78); urinalysis (only at Week 52 and Week 78); urine pregnancy test (where applicable) [refer to [Section 7.1](#)]; HbA1c; and FPG.

Following completion of the above procedures:

- Contact IVRS.
- Provide subject with glucose meter supplies and additional self-monitoring blood glucose or hypoglycemia assessment logs, as needed.
- Subjects will be dispensed drug supplies to last them to the next visit:
 - Double-blind investigational product for ertugliflozin/placebo; AND
 - Blinded glimepiride/placebo therapy (applicable only to subjects who are NOT receiving open-label glimeperide for glycemic rescue).
- Dispense glycemic rescue therapy, if applicable.

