6.7.2. Reasons for Discontinuation from Investigational Product or from the Trial

Reasons for protocol-specified discontinuation from the investigational product or from the trial are listed, but not limited, below. All subjects will be followed until resolution (ie, return to baseline values or diagnosis determined or new stable state established, based upon Investigator and Sponsor [or its delegate] assessment) for any laboratory safety test abnormality resulting in discontinuation from investigational product.

Withdrawal from the Trial

- Subject requests discontinuation from the trial (ie, refuses to continue to be contacted to provide further health information).

090177e1848ce2dd\Approved\Approved On: 23-Sep-2013 15:48

- Death.

Discontinuation of Investigational Product

1. Subject meets protocol-specified hyperglycemia criteria as specified below:

Subject continues to exceed glycemic rescue criteria for at least 3 weeks despite maximal adjustment of basal insulin therapy, without a reasonable explanation (eg, intercurrent illness or medication omission). Subjects who don't agree to start basal insulin will have investigational product discontinued.

2. Hypoglycemia: Repeated (2 or more episodes since the prior visit) FPG or fingerstick glucose <50 mg/dL (<2.8 mmol/L) with or without symptoms of hypoglycemia or ≤70 mg/dL (≤3.9 mmol/L) with symptoms of hypoglycemia, and without a reasonable explanation (such as increased physical activity or skipped meal).

Note: For subjects rescued with glimepiride and/or basal insulin, the protocol-specified discontinuation criteria for hypoglycemia only apply after the subject has interrupted glycemic rescue medication. Similarly, for subjects who were started on Phase B blinded glimepiride or matching placebo, the hypoglycemia criteria only applies when subject is off of blinded glimepiride or matching placebo.

3. Abnormal liver function tests meeting criteria specified in [Section 8.7](#).

4. Parameters of Renal Function:

- Serum creatinine concentrations consistently ≥1.5 mg/dL (133 μmol/L) in men or ≥1.4 mg/dL (123 μmol/L) in women.

OR

- Subjects with eGFR consistently <45 mL/min/1.73 m² (MDRD formula).

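### The hypoglycemia stopping rule in Section 7.4.6.1 omits the exemption in Section 6.7.2 for subjects on rescue medication or blinded glimepiride/placebo, and visit instructions send sites to the version without it

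*Combined protocol and SAP*

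**What the plan says.** Three protocol sections tell sites what to do about repeated hypoglycemia.

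- **Section 7.4.6.1** (Management of Hypoglycemia): "A subject should be discontinued from the investigational product if they have repeated (2 or more episodes since the prior visit", where an episode is a glucose value below 50 mg/dL with or without symptoms, or at or below 70 mg/dL with symptoms, and has no reasonable explanation. The section makes no distinction by background treatment. Its only cross-references are to 6.1.1 and 7.4.6.1.1.
- **Section 6.7.2**, item 2, under discontinuation of investigational product, sets the same thresholds and adds a Note. For subjects rescued with glimepiride and/or basal insulin, the "discontinuation criteria for hypoglycemia only apply after the subject has interrupted glycemic rescue medication". For those started on the Phase B blinded tablets, "the hypoglycemia criteria only applies when subject is off of blinded glimepiride or matching placebo".
- **Section 5.3.5.1**, which covers blinded glimepiride/placebo only, gives a sequence for unexplained hypoglycemia: lower the dose, interrupt it if the subject is already at 1 mg, and then "If unexplained hypoglycemia continues to occur after glimepiride/matching placebo is interrupted, the subject should be considered for discontinuation from the blinded investigational product", with a reference to 6.7.2.

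Investigational product here means ertugliflozin or its placebo, not the glimepiride tablets. Section 5.3.5.1 uses the term that way: "All subjects will continue with investigational product (ertugliflozin/placebo) during Phase B", whether or not the blinded glimepiride/placebo is started at Week 26.

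**The concern.** A subject taking a sulfonylurea or insulin who has repeated low glucose values most plausibly needs less of that drug. Sections 6.7.2 and 5.3.5.1 are built on that logic. Section 7.4.6.1 is not: read alone, it removes ertugliflozin/placebo, which in controls is an inert tablet, and says nothing there about adjusting the glimepiride or insulin.

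The stake is avoidable discontinuation, mainly in Phase B. It would plausibly be unequal between arms, because among non-rescued subjects only the placebo arm receives active blinded glimepiride (Section 5.3.5). Each stop also carries a data cost. Bone biomarker and PTH samples are not to be drawn more than 7 days after investigational product ends (Section 7.7), and are censored if they are (Section 9.2.3.1). Some DXA data may go as well. Discontinuations due to adverse events are reported as a safety outcome (Section 9.3), so that count could depend partly on which section a site had read.

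**Working it through.** No formula applies. The check is a comparison of the rules on one set of facts, followed by a count of where the visit instructions lead.

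**Test case.** Two unexplained, symptomatic glucose values at or below 70 mg/dL since the prior visit.

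| Subject's treatment | 7.4.6.1 | 6.7.2 with Note | 5.3.5.1 |
|---|---|---|---|
| Blinded glimepiride/placebo 4 mg | Stop ertugliflozin/placebo | Criterion not yet in force | Reduce, in general to 2 mg; ertugliflozin/placebo continues |
| Open-label rescue glimepiride or basal insulin | Stop ertugliflozin/placebo | Criterion not yet in force | Does not cover this subject |
| Neither | Stop ertugliflozin/placebo | Stop ertugliflozin/placebo | Does not cover this subject |

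The first two rows conflict and the third agrees. Since the thresholds are identical, the conflict comes entirely from the exemption missing in 7.4.6.1.

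**Where sites are sent.** The log-review step, worded "Review self-monitoring blood glucose and Hypoglycemia Assessment Logs completed by the subject" for Weeks 39 to 91, is followed by a reference to 7.4.6. Counting scheduled visits after Day 1 with that reference:

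- Weeks 6, 12, 18 and 26 (Sections 6.3.2 to 6.3.5): 4
- Week 30 (Section 6.4.1): 1
- Weeks 39, 52, 65, 78 and 91 (Section 6.4.2): 5
- Week 104/early termination (Section 6.4.4): 1

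Total 4 + 1 + 5 + 1 = 11 of 11. After Week 26, 1 + 5 + 1 = 7 of 7. Visit sections citing 6.7.2 or 5.3.5.1: 0 of 11. Footnote y of the Schedule of Activities ("Assess AEs, SAEs, hypoglycemia assessment log as well as potential clinical events for adjudication") likewise refers to 7.4.6, 7.8 and 8. The Week 104/early-termination section and footnote d cite the parent Section 6.7, but for follow-up after stopping. The log-review item at the Rescue Visit (Section 6.6) has no reference.

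**Data lost per avoidable Phase B stop.** The Schedule of Activities has two CTX/P1NP/PTH samples after Week 26, at Weeks 52 and 104.

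- Stop more than 7 days before the Week 52 visit: 2 of 2 lost.
- Stop after Week 52 and more than 7 days before Week 104: 1 of 2 lost.

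An early-termination sample taken within 7 days of the last dose offsets part of this. A DXA scan is done at a Phase B stop if at least 12 weeks have passed since the previous one.

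**Effect on the Week 26 analyses.** Blinded glimepiride/placebo starts no earlier than the Week 26 visit (Section 5.3.5.1). Efficacy data after Phase A rescue are censored in any case (Section 9.2). Stops caused by the conflict therefore have essentially no route into the primary comparison or the testing hierarchy.

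**The case against.** The strongest reply is that the protocol resolves the matter itself. The Note in 6.7.2 speaks of the protocol's hypoglycemia discontinuation criteria in general, 6.7.2 is the section devoted to discontinuation, and 5.3.5.1 defers to it by name. On that reading 7.4.6.1 is an incomplete restatement. This is right about the intent, and the recommended fix relies on it. But no order of precedence is stated, and nothing in 7.4.6.1 leads the reader to the Note.

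A second reply concerns routing. The visit steps cite 7.4.6 for reviewing logs, not as authority for stopping. Section 5.3.5.1 ties glimepiride dose review to Weeks 30 to 91, so a site adjusting the blinded tablets should meet its hypoglycemia steps. Four of the 11 visits (Weeks 6 to 26) come before any blinded glimepiride, so only rescued subjects could be affected there. All of this is fair and lowers the likelihood of error. It does not help subjects on open-label rescue or insulin, whom 5.3.5.1 does not cover. Section 7.4.6.1 is also the subsection headed as managing hypoglycemia, within the section that sites are told to consult.

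Third, all the rules are phrased as recommendations, and Section 7.4.6 says that "appropriate decisions should be made by the Investigator". Discretion softens the instruction but does not cancel a specific contrary one that follows it.

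Finally, counting cross-references measures drafting, not harm. That stands: the count shows that the error is possible, not how often it would happen.

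**Conclusion.** The concern holds. For subjects on glycemic rescue medication or blinded glimepiride/placebo, 7.4.6.1 taken at its word gives the opposite action to the 6.7.2 Note, and for blinded glimepiride/placebo also to 5.3.5.1. It is an internal inconsistency rather than a disputed design decision, and it should be corrected.

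Its size is modest. How many subjects would be affected cannot be obtained from the documents, and no rate is assumed here. That non-rescued controls would be stopped more often is an inference from their being the only non-rescued subjects on active glimepiride, and it assumes that some sites apply 7.4.6.1 literally. The Week 52 and 104 bone objectives concern the ertugliflozin arms (Section 2.1) and the results are summarized descriptively (Section 9.2.3.1), so losses among controls mainly weaken the descriptive control summary. Stopped subjects may continue clinic visits (Section 6.7) and are asked back at Week 104 (Section 6.7.2), which limits the loss of DXA data.

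**What to change.** Replace the stand-alone rule in 7.4.6.1 with one sentence: for discontinuation of investigational product because of hypoglycemia, see Section 6.7.2 including its Note; for subjects on blinded glimepiride/matching placebo, first follow Section 5.3.5.1. Copying the 6.7.2 Note into 7.4.6.1 would serve as an alternative.

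The cost is a one-sentence protocol clarification. Design, sample size and analysis stay as they are.
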